6.9.1. Primary Objective

The study hypothesis for the primary objective is to verify whether DDD patients operated for spondylolisthesis (\geq grade I) have equivalent mean improvement of ODI at 3 months regardless of anterolateral or posterior procedure used.

The hypothesis includes:

$$H_0: \Delta_{ODI_anterolateral} \neq \Delta_{ODI_posterior}$$

$$H_a: \Delta_{ODI_anterolateral} = \Delta_{ODI_posterior}$$

This document is electronically controlled. Printed copies are considered uncontrolled.

Confidential

Where $\Delta_{ODI_anterolateral}$ is the average improvement in ODI score (baseline – 3 months) in spondylolisthesis subjects treated with the anterolateral approach and $\Delta_{ODI_posterior}$ is the average improvement in ODI score (baseline – 3 months) in spondylolisthesis subjects treated with the posterior approach.

ANCOVA will be performed with baseline ODI as covariate and the two-sided 95% CI for the least square mean difference of ODI improvement between two groups at 3 months will be calculated. If the 95% CI is within the equivalent range of (-10, 10), then the primary objective is met. In addition, the paired t-test will be carried out for each group to see whether the ODI improvement at 3 months from baseline is significant.

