#### **B.1.4 Additional Measurements**

Other measurements in the study will be co-morbidities, hospital discharge day, rehabilitation program, pain medication consumption throughout the study, days to first return to work, additional medical visits related to back pain, sagittal balance.

Co-morbidities

Comorbidities can be either medical condition(s) existing simultaneously but independently with another condition; or it can indicate a related medical condition or conditions. Comorbidities may affect the outcomes of the surgery.

Hospital Discharge Day

Days after the surgery when patient has been discharged from hospital.

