## B.5 Study design

The MASTERS-D 2 study is a Prospective, Global clinical trial. Commercially available study devices will be used within their intended use.

The indication for the treatment of a patient will be at the discretion of the surgeon.

As such the assignment of a patient to a particular surgical intervention is not required within this clinical study protocol but falls within standard of care practice.

All fusion procedure patients will be screened consecutively against the eligibility criteria. Every effort will be made to enroll subjects in a consecutive manner.

Study enrollment is open to eligible subjects who in the opinion of the investigator are candidates for a minimally invasive lumbar fusion surgery.

The investigator or authorized designee must obtain written informed consent/ data release consent from the patient before any clinical study related activity takes place. The patient has the right to refuse and refusal will not affect the care of the patient. The patient can opt out at any time from the study. Refusal of study participation as well as enrollment into the study will be recorded on the screening log.

The following measures have been taken to avoid bias:

- Consecutive screening and enrollment is encouraged and enforced as much as possible.
  - When all inclusion/exclusion criteria are fulfilled for a patient, then the patient should be enrolled in this study. A screening log will be maintained at each site documenting the patients that have been screened and identified to be eligible or ineligible for the study, declined patients and enrolled patients.
  - In case the group with one of the approach procedures has reached the maximum amount of patients per procedure in a specific region, further enrollment of subjects into the procedure will be terminated. An email will be sent to the participating sites to inform the investigators when the enrollment for a specific procedure is complete.
- A multi-center design is used to help ensure a representative sample of surgeons performing the procedure and to ensure a reasonable enrollment period
- Only surgeons that have adequate experience (> 30 minimally invasive lumbar fusion procedures) can participate
- Site training will be performed to assure full understanding and engagement to comply with the study design and all protocol requirements

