## B.6 Randomization and blinding

Randomization and blinding is not applicable in this study.

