It is expected that approximately 350 patients will be enrolled in this study from approximately 30 sites in Europe, Middle East, Latin America and Asia Pacific. This study will be open for enrollment to other countries in order to meet the required patient numbers. Sites have been selected based upon an anticipated enrollment for each minimally invasive fusion procedure. Consecutive enrollment will apply per minimally invasive procedure (i.e. ALIF, OLIF, DLIF, PLIF, TLIF and or MIDLF).

To allow the different regions to contribute patients to this study, a maximum enrollment per country/region might be defined during the course of the study. This will be timely communicated to the investigators and they will be requested to stop enrollment when the country/regional anticipated maximum number of patients has been reached. Patient enrollment limits per site for each country/region are indicated in Table 1. These limits may be subject to change during the course of the study and will be communicated as appropriate to the investigators and EC/IRB, if required.

The distribution of the procedures differs among the regions. Patient distribution across different surgical procedures will be in accordance with natural distribution in the country, but the study will aim to balance the

subjects between the procedures. Nevertheless, a minimum enrollment of 20 patients in each procedure (ALIF, OLIF, DLIF, PLIF, TLIF or MIDLF) is required for the study. A broad usage of both anterolateral and posterior lumbar fusion procedures is encouraged at all sites even though it is acknowledged that a user preference will apply. Enrollment limits per procedure have been defined for sites in China as these sites are allowed to enroll more patients than sites in other regions (Table 1). Investigators will be requested to stop enrollment when the maximum enrollment for that procedure at their site has been reached.

**Table 2: Overview of patient enrollment limits in Europe, Latin America, Middle East and Asia Pacific per site and per procedure.**

REGION	EUROPE	LATIN AMERICA	CHINA	KOREA
Enrollment max per site	40	20	120	20
Enrollment maximum per procedure for each site*	40	20	75	20
Estimated Number of sites	21	3	3	3

\* Enrollment limits per procedure might change to obtain a better distribution of procedures amongst the sites and regions and reach the minimum enrollment of 40 patients in each procedure. Any change in enrolment limitations will be communicated to the sites.

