## C SUBJECT SELECTION

### C.1 Inclusion and exclusion criteria

The **Inclusion Criteria** for this study are:

- Patient is  $\geq$  18 years of age (or minimum age as required by local regulations)
- Patient has degenerative disc disease and an indication for a single or double level instrumented lumbar fusion for the treatment
- Patient agrees to participate in the study and is able to sign the Data Release Form/Informed Consent
- The procedure planned for the patient complies with the labeling of the Devices that may be used in the surgical procedure as described in the section **Device information** above
- Patient is planned to be submitted to a minimally invasive fusion procedure using a **posterior (PLIF, TLIF, MIDLF) or anterolateral (OLIF, ALIF, DLIF) technique\***.
- The patient is willing and is able to perform study procedures and required follow-up visits.

\* For a double level instrumented fusion, the same procedure must be used for both levels.

The **Exclusion Criteria** for this study are:

- Patient that has already undergone a lumbar fusion surgery
- Patient that has already undergone open lumbar surgery other than standard decompression surgery
- Indications for the procedure other than degenerative spine disease like: Osteoporotic vertebral fractures, Spine trauma fractures or Spine tumor
- Illiterate or vulnerable patients (e.g. minors, participants incapable of judgment or participants under tutelage)
- Concurrent participation in another clinical study that may confound study results.

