## **E.3 Baseline procedures**

During the baseline visit the following data will be collected, patient demographics, medical history, comorbidities, surgery indication, pain medication, work status, imaging data. A standardized visual analogue scale (VAS, 0-10) will be used to evaluate the level of leg and back pain as perceived by the patient prior to surgery. Quality of life will be assessed having the patient completing the EQ-5D. Evaluation of how back or leg pain is affecting the patient's ability to manage in everyday life will be assessed using the Oswestry Disability Questionnaire (ODI). Neurological status; in case of a neurological abnormality, the neurological status will be assessed and documented. The measurement of Slip and Disk Height of the levels adjacent to the index level(s) will be collected by X-Ray, CT scan and/or MRI whichever is applicable at the site. The identification of neuropathic pain will be assessed by the DN4 questionnaire in the back and in the leg.

Sagittal Balance will be collected in those sites where it is standard of care by collecting an X-Ray (preferably this would be a long standing / full spine X-Ray (C7 + Femoral Head visible) or alternatively a short X-Ray with the femoral heads and top of lordotic segment visible).

AEs should be collected after patient signed consent/data release form.

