#### **G.1.1 Analysis of Primary Endpoint**

To evaluate whether the primary endpoint improvement in ODI at 3 months is equivalent for the spondylolisthesis DDD subjects treated with anterolateral approaches and the ones treated with posterior approaches, the two-sided 95% confidence interval for the mean difference of ODI improvement at 3 months will be calculated. If the 95% CI is within the equivalent range of (-10, 10), then the primary objective is met. In addition, the paired t-test will be carried out for each group to see whether the ODI improvement at 3 months from baseline is significant.

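### Surgeons choose the approach, but the CI that decides equivalence adjusts for baseline ODI only, and no required sensitivity analysis covers other measured case mix

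*SAP*

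**What the plan says.** **Allocation.** Protocol B.6 states: "Randomization and blinding is not applicable in this study". Protocol B.5 leaves the procedure to standard of care: "the assignment of a patient to a particular surgical intervention is not required within this clinical study protocol". On the use of both approaches, Protocol B.7 says "anterolateral and posterior lumbar fusion procedures is encouraged at all sites even though it is acknowledged that a user preference will apply", and it adds that the mix of procedures differs between regions.

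**Deciding analysis.** Protocol G.1.1 names no covariate: "the two-sided 95% confidence interval for the mean difference of ODI improvement at 3 months will be calculated". SAP 6.9.1 is more specific: "ANCOVA will be performed with baseline ODI as covariate and the two-sided 95% CI for the least square mean difference of ODI improvement". The objective is met if that interval lies within (-10, 10). Protocol G.1.4 makes the primary conclusion final at the 3-month analysis.

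**Other measured factors.** Protocol B.1.4 says: "Comorbidities may affect the outcomes of the surgery". Eligibility is broad: "Patient has degenerative disc disease and an indication for a single or double level instrumented lumbar fusion for the treatment". Protocol E.3 collects, among other items, "patient demographics, medical history, comorbidities, surgery indication, pain medication, work status, imaging data", together with VAS back and leg pain.

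**The concern.** Without randomisation, nothing makes the two approach groups alike in anything but baseline ODI, which the model handles. The documents themselves give reasons to expect differences. Surgeons have preferences and regions differ in procedure mix (Protocol B.7). Some procedures are tied to particular disc levels (Protocol B.3). Documenting which patients receive which procedure is itself a secondary objective (Protocol B.1.3). They also name a measured factor, comorbidity, that may influence outcome.

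In an equivalence comparison, bias can favour the claim. A case-mix difference that offsets a real difference between approaches produces a false finding of equivalence, and one in the other direction hides true equivalence. The claim rests on one interval, and its verdict is not reopened at the final analysis.

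**Working it through.** **Step 1. Does anything in the plan adjust the pooled deciding CI for other case mix?**

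- Baseline tables by approach (SAP 6.6): these show imbalance but do not change the interval.
- Region (SAP 6.3): an ANCOVA with region, approach, their interaction and baseline ODI tests poolability. If region is not significant, data are pooled and the 6.9.1 model has no region term. If it is significant, results are shown by region. A non-significant test does not rule out confounding by region, and says nothing about other factors.
- Stenosis subgroups, and optional subgroups by number of levels (SAP 6.1.3): separate analyses outside the decision rule.
- Consecutive screening and enrolment (Protocol B.5, E.1): limits selection into the study, not selection between approaches.
- Sensitivity analysis on the primary endpoint (SAP 6.9): changes the visit windows only.
- Regressions on pathology and approach (SAP 6.9.3, item 8): optional, and ODI is not among the outcomes named.

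Each is partial, and none adjusts the pooled deciding CI.

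**Step 2. The plan's own figure.** Inputs from SAP 5: SD 20, margin 10, true difference 0, 80% power, 5% alpha, 70 per group. Two one-sided tests at 5% each give n = 2 × [20 × (1.645 + 1.282)/10]² = 68.5, or 69. The t-based power at 70 is 80.6%, so 70 reproduces. The rule in SAP 6.9.1 uses a 95% CI, under which 70 per group gives 67.2%. That mismatch is a separate matter. It enters here only because 67.2% is the correct no-bias reference for the rule as written.

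**Step 3. Room for error at 70 per group.** SE = 20 × √(2/70) = 3.38. Half-width = t(138; 0.975) × SE = 1.977 × 3.38 = 6.68. At SD 20 the estimate must lie within about 10 - 6.68 = 3.32 points of zero.

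**Step 4. Illustration with an assumed bias.** Bias here means what remains after baseline-ODI adjustment. For a yes/no factor unrelated to baseline ODI, bias = difference in prevalence × effect on ODI improvement. For example, 0.30 × 10 = 3 points, which is a severe case because the factor is worth the whole margin. The pass probability is P(|estimate| + half-width < 10), integrated over the sampling distribution of the variance, with expected estimate = true difference + bias.

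| Residual SD | True difference | No bias | Bias of 3 |
|---|---|---|---|
| 20 | 10 (bias towards 0) | 2.5% | 13.9% |
| 20 | 0 | 67.2% | 50.7% |
| 17 | 10 (bias towards 0) | 2.5% | 17.8% |
| 17 | 0 | 86.5% | 67.1% |

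Smaller biases do less. At SD 20 and a true difference of 10, 1 point gives 4.8% and 2 points give 8.5%.

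**Step 5. Precision of an adjusted model.** If the added covariates explain a share R² of approach choice and none of the outcome, half-width = 6.68/√(1 - R²). For R² of 0.10, 0.20 and 0.30 this is 7.05, 7.47 and 7.99. Covariates that also predict outcome offset the loss: 20% of approach and 20% of outcome returns it to 6.68.

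**The case against.** The strongest reply is that the plan is not blind to case mix. Baseline ODI is likely to absorb part of any imbalance. Approach groups are tabulated side by side, region has its own rule, stenosis strata are analysed, enrolment is meant to be consecutive, and the primary population is restricted to spondylolisthesis. The list of outcomes in SAP 6.9.3 is not exhaustive, so a regression on ODI is not ruled out. All of this stands, and it makes the gap narrower than a wholly unadjusted comparison. It does not close it, because the optional analyses may never be run and the required ones do not adjust the interval.

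The reply on magnitude also stands. Every bias above is assumed. The false-equivalence figures place the true difference exactly at the margin, whereas planning assumed 0. A residual SD below 20 gives better success rates. If all 350 patients enrol and half have spondylolisthesis, there would be about 350 × 0.5/2 = 87 per group if balanced and without loss, giving about 81% success with no bias. Protocol B.7, however, allows enrolment to stop at the required number.

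Three stronger readings should be resisted:

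- **That the deciding comparison is crude.** Protocol G.1.1 names no covariate, but the SAP is the operative text and includes baseline ODI.
- **That the equivalence verdict will be wrong.** The documents give no imbalance and no covariate effect, so neither the direction nor the size of bias is known.
- **That equivalence should require both the baseline-ODI and the adjusted CI to meet the margin.** In a simulation with the assumed factor of Step 4, uncorrelated with baseline ODI, false equivalence was 2.5% for the adjusted CI alone and 2.4% for both. Under true equivalence, success was 63.5% adjusted, 50.7% with baseline ODI only and 35.9% for both. A two-interval rule gains almost nothing and lets the more confounded interval veto the better one.

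**Conclusion.** The gap is certain from the text: approach is surgeon-chosen, and the pooled interval that decides equivalence adjusts for no measured factor except baseline ODI. Following the plan exactly could therefore yield a biased verdict in either direction, with no required analysis to reveal it. The size is unknown. The 3-point illustration (2.5% to 13.9% false equivalence at a true difference of 10; 67% to 51% success at 0, or 87% to 67% if the residual SD is 17) shows sensitivity under assumptions and is not an estimate for this trial. The point merits a change to the SAP, but it does not show that the planned primary analysis must be replaced.

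**What to change.** Before the 3-month analysis, add to SAP 6.9.1 a mandatory, prespecified adjusted sensitivity analysis of the primary endpoint:

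- **Model:** ANCOVA of ODI improvement on approach, with baseline ODI, region (using the Latin America merging rule of SAP 6.3), stenosis, spondylolisthesis grade, age, number of comorbidities, and baseline VAS back and leg pain.
- **Number of levels:** include the planned number if it was recorded before surgery. Levels treated (SAP 6.7) may follow from the choice of approach, so use it only in a further run.
- **Disc level:** the sponsor should also consider this, because Protocol B.3 ties some procedures to particular levels.
- **Missing covariates:** use complete cases, in line with SAP 6.4, and rerun the baseline-ODI model on the same patients.
- **Reporting:** show both models side by side and state in the conclusion whether they agree. If they do not, say that the conclusion depends on adjustment. State in either case that unmeasured confounding remains. Do not require both intervals to meet the margin.
- **Documentation:** SAP 6.12 is marked not applicable; record there the departure from Protocol G.1.1. If the 3-month analysis has already been run, label the adjusted model post hoc.

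The cost is SAP wording and modest programming, since most covariates are already collected at baseline. Some patients may be lost from the adjusted model through missing covariates. Its interval may be wider if the covariates predict approach more than outcome (half-width from 6.7 to about 7.0-8.0 under the assumed R² of 10-30%). The deciding CI is unchanged and loses no power.

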6.9.2. Secondary Objectives

6.9.2.1. To evaluate whether DDD patients without spondylolisthesis fare equally well regardless of the surgical procedure (anterolateral or posterior) performed, as measured by ODI at 3 months

The similar method as the one outlined above for the primary endpoint will be used to assess whether the ODI improvement at 3 months is equivalent for the non-spondylolisthesis subjects treated with anterolateral approaches and the ones treated with posterior approaches.

6.9.2.2. To observe and document clinical and radiological outcomes through 5-year follow-up (except for ODI at 3 months)

The following analyses will be carried out for both the primary dataset and subgroup datasets defined in section 6.1.3.

6.9.2.2.1. Improvement of ODI / VAS back and leg pain intensity / EQ -5D as compared to baseline

Summary statistics (mean, standard deviation, median, minimum and maximum) will be presented for the ODI / VAS back and leg pain intensity / EQ-5D at baseline and each follow-up (except for ODI at 3 months), and the improvement of the ODI / VAS back and leg pain intensity / EQ-5D at each follow-up through 5-year visit (except for ODI at 3 months) from baseline. Paired t-test will be performed to see whether the improvement is significant.

6.9.2.2.2. Neurological success

Neurological status is based on four sections: motor, sensory, reflexes, and straight leg raising. Each of the sections is comprised of a number of elements.

6.9.2.2.2.1 Motor Function

For the motor function, the assessments are listed in ascending order of improving as indicated below:

0 = Total Paralysis

1 = Palpable or Visible Contraction

2 = Active Movement, Gravity Eliminated

This document is electronically controlled. Printed copies are considered uncontrolled.

Confidential

3 = Active Movement, Against Gravity

4 = Active Movement, Against Some Resistance

5 = Active Movement, Against Full Resistance (full strength) (Normal)

For the time period evaluated, for each of elements, if the score increases from baseline, the subject is considered "improved"; if the score remains the same as baseline, the subject is considered "maintained"; if the score decreases from the baseline, the subject is considered "deteriorated". In the situation where the score at baseline is 0 (Total Paralysis) and a postoperative visit is missing, or the score at baseline is missing and at a postoperative visit is 5 (Normal), the subject is conservatively considered as "maintained". For overall motor status, if at least one element has the status of "improved" and the rest are "maintained", then the overall motor status is considered "improved"; if all elements have the status of "maintained", then the overall motor status is "maintained"; if at least one element has the status of "deteriorated", then the overall motor status is "deteriorated."

6.9.2.2.2.2 Sensory function (Light Touch or Pin Prick L1 to S1)

For the sensory function, the assessments include absent, impaired and present (normal) which are listed in ascending order of improving. Let absent be 0, impaired be 1 and normal be 2. The same logic outlined in the motor function section will be used to first determine the change status of each element from the baseline and then the overall sensory status from the baseline. For each element, in the situation where the score at baseline is 0 (Absent) and a postoperative visit is missing, or the score at baseline is missing and at a postoperative visit is 2 (Normal), the subject is conservatively considered as "maintained".

6.9.2.2.2.3 Reflexes

For the reflexes, the assessments are listed as indicated below:

0 = Absent or Trace

1 = Hyper-reflexic

2 = Normal

For each element, a change from 0 (Absent or Trace) to 2 (Normal) or 1 (Hyper-reflexic) to 2 (Normal) is considered improved while the other way around is considered deteriorated. No change is considered maintained. Any change from 0 (Absent or Trace) to 1 (Hyper-reflexic) is considered "diminished to hyperactive" while the other way around is considered "hyperactive to diminished". In the situation where the score at baseline is missing and at a postoperative visit is 2 (Normal), the subject is conservatively considered as "maintained". If none of element has the situation of "diminished to hyperactive" or "hyperactive to diminished", an overall evaluation of reflex will be summarized using the same logic outlined in the motor function section. Otherwise, there will be no overall evaluation.

6.9.2.2.2.4 Straight leg raise

For the straight leg raise, the assessments include positive and negative (normal). Let positive be 0 and negative be 1. The same logic outlined in the motor function section will be used to first determine the

This document is electronically controlled. Printed copies are considered uncontrolled.

Confidential

change status of each element from the baseline and then the overall straight leg raise status from the baseline. For each element, in the situation where the score at baseline is 0 (Positive) and a postoperative visit is missing, or the score at baseline is missing and at a postoperative visit is 1 (Negative), the subject is conservatively considered as "maintained".

Overall neurological success will be defined as maintenance or improvement in all sections (motor, sensory, reflex, and straight leg raising) for the time period evaluated. In order for a section to be considered a success, each element in the section must remain the same or improved from the time of the baseline evaluation to the time period evaluated. If at least one section is deteriorated, the overall neurological success will be defined as failure.

Summary statistics (frequencies) will be presented for status of each section and overall neurological success at each follow-up.

